
Q2W = Every 2 weeks, IV = Intravenous
**Priming dose will be given over 3 hours (+/- 30 minutes)*
***Hu5F9-G4 (magrolimab) to be administered before mogamulizumab on days when both treatments are given*
**** Within 24 hours prior to each of the first 2 doses of Hu5F9-G4 infusion, patients must have a documented hemoglobin level of ≥ 9 g/dL. Patients who do not meet these criteria must be transfused and have their hemoglobin rechecked to meet the minimum hemoglobin threshold prior to administering each of the first 2 doses of Hu5F9-G4. An additional hemoglobin must be checked 3 to 6 hours after the initiation of the first and second doses of Hu5F9-G4. The patient should be transfused as clinically appropriate. Investigators should consider additional hemoglobin monitoring during the first week of treatment in patients with symptoms of anemia or at increased risk for complications of anemia.*

Table 4: Regimen Description for Phase 2 (Mogamulizumab Only Arm)

Regimen Description					
Agent	Premedication; Precautions	Dose	Route	Schedule	Cycle Length
Mogamulizumab	650-1,000 mg acetaminophen oral (PO) and 25 mg diphenhydramine	1 mg/kg	IV	Weekly for cycle 1, then Q2W starting from cycle 2	28 days (4 weeks)

	(PO or IV) or a comparable regimen at least 15 minutes before the first dose of mogamulizumab.				
Q2W = Every 2 weeks, IV = Intravenous					

For patients who crossover to the Hu5F9-G4 (magrolimab)/mogamulizumab combination due to progression or lack of response after 6 months, no washout will be required and treatment will proceed with an identical schedule as the combination arm starting with the priming dose of Hu5F9-G4 (magrolimab).

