6.1.1 CTEP IND Agent

6.1.1.1 Hu5F9-G4 (magrolimab)

All cohorts in both phase 1B and phase 2 portion will follow the same dosing schedule, though the dose of Hu5F9-G4 (magrolimab) may vary, following the de-escalation design of the phase 1B portion (see Table 2). For patients receiving the combination of Hu5F9-G4 (magrolimab) and mogamulizumab, treatment will start with a priming dose of Hu5F9-G4 (magrolimab) of 1mg/kg IV without mogamulizumab. Starting one week later, patients will receive the designated dose of Hu5F9-G4 (magrolimab) (either 30mg/kg or 20mg/kg IV) every week for eight weeks. After the first 8 weeks, the schedule of Hu5F9-G4 will change to every 2 weeks ongoing. Mogamulizumab treatment will also start one week after the priming dose of Hu5F9-G4 (magrolimab) at the FDA-approved dose and schedule.

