- $2^{\circ}\text{C} - 8^{\circ}\text{C}$ (36°F to 46°F) for up to 16 hours, which includes the preparation time and the completion time of the infusion including 1 hour for IV solution to equilibrate at room temperature before administration. Discard IV if exceeding 16 hours.

Storage: Store vials at $2^{\circ}\text{C} - 8^{\circ}\text{C}$ (36°F to 46°F) in the original carton, protected from light. Do not freeze.

If a storage temperature excursion is identified, promptly return Hu5F9-G4 (magrolimab) to $2^{\circ}\text{C} - 8^{\circ}\text{C}$ (36°F to 46°F) and quarantine the supplies. Provide a detailed report of the excursion (including documentation of temperature monitoring and duration of the excursion) to [contact] for determination of suitability.

Stability: Shelf-life stability studies of the intact or unused vials are on-going.

CAUTION: The single-use injectable vial contains no antibacterial preservatives. Therefore, it is advised that the reconstituted product be discarded 8 hours after initial entry.

Route of Administration: Intravenous. Do not administer as an IV bolus.

Method of Administration: A priming dose of Hu5F9-G4 (magrolimab) is required 1 week prior to Cycle1 Day1. The priming dose (1 mg / kg) will be infused over 3 hours (+/- 30 minutes) via a

NCI Protocol #: 10384

Version Date: September 5, 2023

peripheral or central line through a polyethersulfone (PES) in-line IV filter set. Prime the IV line with the prepared IV solution before starting the infusion. After completing the infusion, the IV line can be flushed with 40 mL normal saline at the same infusion rate in the table below or as per institutional guidelines. Subsequent IV doses are to be infused over 2 hours (+/- 10 minutes).

Dose	Infusion volume (mL)	Infusion time	Rate (mL/min)	Rate (mL/Hour)
1 mg/Kg	250	3 hours (+/- 30 mins)	1.4	83
15 mg/Kg	500	3 hours (+/- 30 mins)	2.8	167
30 mg/Kg	500	2 hours (+/- 30 mins)	4.2	250

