9.4 Analysis of Secondary Endpoints

The analysis plan for the secondary objectives will be as follows:

Table 5: Analysis of Secondary Endpoints

Secondary Endpoint	Statistical Method
ORR, ORR4, ORR12	Chi-squared
PFS, DOR, TTNT	Kaplan-Meier method; Log- rank

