11. STUDY CALENDAR

Baseline evaluations are to be conducted within 1 week prior to start of protocol therapy. Scans and x-rays must be done \leq 4 weeks prior to the start of therapy. In the event that the patient's condition is deteriorating, laboratory evaluations should be repeated within 48 hours prior to initiation of the next cycle of therapy.

	Pre-Study	Priming	Cycle 1 ^m					Cycle 2 ^m					Cycle 3 ^m		Cycle 4-12 ⁿ		End of Treatment or Progression ^a
			Wk 1	Wk 1	Wk 2	Wk 3	Wk 4	Wk 1	Wk 2	Wk 3	Wk 4	Wk 1	Wk 3	Wk 1	Wk 3		
Hu5F9-G4 (magrolimab)		A	A	A	A	A	A	A	A	A	A	A	A	A	A		
Mogamulizumab			B	B	B	B	B		B			B	B	B	B		
Informed consent	X																
Demographics	X																
Medical history	X																
Concurrent meds ^b			X-----										X			X	
Physical exam	X	X	X	X	X	X	X	X	X	X	X	X	X	X		X	
Vital signs	X	X	X	X	X	X	X	X	X	X	X	X	X	X		X	
Height	X																
Weight	X	X	X				X					X		X			
Performance status ^c	X	X	X	X	X	X	X		X			X		X		X	
CBC w/diff, plt ^p	X	X ^p	X ^p	X	X	X	X	X	X	X	X	X	X	X			
Comprehensive Chemistry Panel ^d	X	X	X	X	X	X	X	X	X	X	X	X	X	X			
Pregnancy test ^e	X																
ABO/Rh type and screen, DAT ^f	X																
Antibody Screen ^g	X																
Extended RBC phenotyping including minor antigens such as CcDEe, Cw, MNSs, Kk, FyaFyb, and Jka Jkb ^{h,i}	X																
Adverse event evaluation			X-----										X			X	
mSWAT assessment/medical photography ^f		X						X					X	X ^f		X	
Imaging ^g	X												X ^g	X ^g		X ^g	
Flow Cytometry		X											X ^h	X ^h		X ^h	
FFPE biopsy tissue (optional)	X ^o																
Skin punch biopsies ^l	X			X								X				X	
Correlative blood collection ^k	X			X								X	X			X	

	Pre-Study	Prim ing	Cycle 1 ^m				Cycle 2 ^m				Cycle 3 ^m		Cycle 4-12 ⁿ		End of Treatment or Progression ^a
			Wk 1	Wk 1	Wk 2	Wk 3	Wk 4	Wk 1	Wk 2	Wk 3	Wk 4	Wk 1	Wk 3	Wk 1	Wk 3
A:	Hu5F9-G4 (magrolimab) : On Priming Week 1 only, a priming dose of 1 mg/kg Hu5F9-G4 (magrolimab) will be given. Then assigned dose on Cycle 1 Day 1, 8, 15, and 22, Cycle 2 Day 1, 8, 15 and 22, Cycle 3+ Day 1, 15. Cycles are 28 days long.														
B:	Mogamulizumab: 1mg/kg on Cycle 1 Day 1, 8, 15, and 22, Cycle 2+ Day 1, 15. Cycles are 28 days long.														
a:	Off-study evaluation. Cycle 12 (Week 48) visit may serve as end of treatment/progression visit														
b:	Starting from cycle 4, concurrent meds will be evaluated first week of every cycle														

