c:	Note: Performance status evaluations are based on a 4 week cycle. At minimum, performance status should be evaluated at the beginning of every cycle.														
d:	Albumin, alkaline phosphatase, total bilirubin, bicarbonate, BUN, calcium, chloride, creatinine, glucose, potassium, total protein, SGOT [AST], SGPT [ALT], sodium.														
e:	Pregnancy test for women of childbearing potential.														
f:	Starting from Cycle 6, mSWAT assessment will be performed on the 1 st week of every 3 rd cycle (i.e. cycle 6, 9, 12, 15, etc.), and at the end of treatment or progression.														
g.	Patients without extracutaneous disease at screening (N0-2 and M0): scans will be performed at baseline and repeated to confirm global PR/CR, at suspicion of PD. Patients with extracutaneous disease at screening (N3 or Nx or M1): scans will be performed at baseline, Week 12, and then repeated at the end of every 3 cycles (i.e. cycle 6, 9, 12.), to confirm global PR/CR, at suspicion of PD. Scans at the time of progression or at the end of treatment do not need to be repeated if the most recent scan occurred within the past 28 days. End of cycle scans should be performed between Days 15 and 28, or Day 1 of the following cycle. Either PET/CT or diagnostic CT chest/abdomen/pelvis +/- neck may be used. Visit windows of \pm 7 days allowed.														
h.	Patients with B1 or B2 disease at baseline: Flow cytometry will be performed at Week 1, Week 12, and then repeated on the 1 st week of every 3 rd cycle (i.e. cycle 6, 9, 12). Flow cytometry will also be performed to confirm global PR/CR, if progression of disease is suspected and at end-of-treatment. Patients with B0 disease at baseline: Flow cytometry will be performed at baseline, to confirm a partial or complete response, if progression of disease is suspected, and at end-of-treatment.														
j.	Biopsies are not required for patients with a complete response in the skin.														
k.	Correlative blood collection will be performed at baseline, Cycle 1 Week 2, Cycle 3 Week 3, Cycle 6 Week 1, and at PD/EOT.														
l.	ABO/Rh, RBC genotyping, and DAT testing are not required for patients randomized to the mogamulizumab-only arm. This will be done prior to crossover to the combination arm if applicable.														
m.	For cycle 1 through cycle 3, visit windows of \pm 2 days allowed														
n.	Starting from cycle 4, visit windows of \pm 3 days allowed														

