12.2 Definitions of Study Endpoints

Overall Response Rate (ORR): ORR is defined as the proportion of patients who have a partial or complete response to therapy as defined by the global response score.

Duration of Response (DOR): DOR is defined as the duration of overall response is measured from the time measurement criteria are met for CR or PR (whichever is first recorded) until the first date that recurrence or PD is objectively documented.

Overall Response Rate 4 (ORR4): ORR4 is defined as the proportion of patients who have a partial or complete response to therapy AND a duration of response \geq 4 months.

Overall Response Rate 6 (ORR6): ORR6 is defined as the proportion of patients who have a partial or complete response to therapy AND a duration of response \geq 6 months.

Overall Response Rate 12 (ORR12): ORR12 is defined as the proportion of patients who have a partial or complete response to therapy AND a duration of response \geq 12 months.

Progression-Free Survival (PFS): PFS is defined as the duration of time from start of treatment to time of progression or death, whichever occurs first.

Time to next treatment (TTNT): TTNT is defined as the duration of time from the start of treatment on this protocol to time of the next anti-neoplastic therapy.

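### Only the combination arm has a priming week, so cycle-counted assessments fall about 7 days later on its PFS clock and tilt the secondary log-rank by an amount the documents cannot fix

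*Combined protocol and SAP*

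**What the plan says.** Section 12.2: "PFS is defined as the duration of time from start of treatment to time of progression or death, whichever occurs first". Table 5 in Section 9.4 gives the PFS method as "Kaplan-Meier method; Log- rank", with no level, sidedness or censoring date. The one-sided 15% in Section 9.1 belongs to ORR6.

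The arms start differently. For the combination, Section 6.1.1.1 says "treatment will start with a priming dose of Hu5F9-G4 (magrolimab) of 1mg/kg IV without mogamulizumab", and Section 8.1.1 adds "A priming dose of Hu5F9-G4 (magrolimab) is required 1 week prior to Cycle1 Day1". The control regimen (Section 6.1, Table 4, whose title begins "Regimen Description for Phase 2 (Mogamulizumab Only Arm") goes straight into Cycle 1.

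Assessments follow the cycle count in both arms (Section 11):
- **Skin (footnote f):** "Starting from Cycle 6, mSWAT assessment will be performed on the" first week of every third cycle.
- **Blood (footnote h):** flow cytometry for patients with B1 or B2 disease follows the same pattern after Week 12.
- **Scans (footnote g):** patients with extracutaneous disease are scanned at Week 12 and then at the end of every third cycle: "End of cycle scans should be performed between Days 15 and 28, or Day 1 of the following cycle", with a further 7 days either side.
- **Week count (footnote a):** "Cycle 12 (Week 48) visit may serve as end of treatment/progression visit".

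**The concern.** The PFS clock starts at priming in one arm and at Cycle 1 Day 1 in the other, but the assessments are anchored to cycles. A log-rank test works on the order of events. When progressions take the date of a scheduled visit, they cluster by round, and the control cluster comes about a week before the combination cluster. Control events are then counted while combination patients who have also progressed still stand as event-free. The lean always favours the experimental arm, and nothing in Sections 9.4 or 12.2 corrects it.

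PFS is a named secondary efficacy comparison (Section 1.2). What is at stake is whether a modest PFS advantage could be told apart from a scheduling artefact.

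**Working it through.** **Plan's own figure.** The plan gives no operating characteristic for PFS. Its Phase 2 power figure is for ORR6 (Section 9.1: 41 per arm, odds ratio 3.2, one-sided 15%, power 86%), and it reproduces. The odds ratio turns 30% into 57.8% and 10% into 26.2%; 0.3 × 57.8 + 0.7 × 26.2 = 35.7%, the plan's 36%. A stratified normal approximation gives 86.0–86.7% power. Using 15% for PFS is an assumption.

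**Step 1: the clock.** Day 1 of Cycle k falls 28 × (k − 1) days after start of treatment on control and 7 + 28 × (k − 1) days on the combination. Cycle 6 is day 140 against 147, Cycle 9 is 224 against 231, and Cycle 12 is 308 against 315. Twelve cycles take 12 × 28 = 336 days = 48 weeks, so the label in footnote a leaves the priming week out.

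**Step 2: one round by hand.** Take 41 per arm, no drug effect, a 7.7-month median (the mogamulizumab figure in Section 9.1) and one 12-week round (84 days = 2.76 months). The share progressing is 1 − 0.5^(2.76/7.7) = 0.22, or about 9 per arm.
- Same date in both arms: expected on the combination = 18 × 41/82 = 9.00; observed 9.
- Control dated first: expected = 9 × 41/82 + 9 × 41/(82 − 9) = 4.50 + 5.05 = 9.55; observed 9.

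The combination shows a deficit of 0.55 events with no drug effect. The same happens in later rounds among those still at risk.

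**Step 3: simulation.** 20,000 trials per setting, 41 per arm, exponential PFS with a 7.7-month median in both arms. Accrual is 82/4 = 20.5 months (Section 9.2) plus an assumed 12 months, giving uniform censoring at 12–32.5 months. Dates are whole days, and the test rejects in favour of the combination when z < −1.036. Unless the row says otherwise, the offset is 7 days, windows are 2–3 days and there are no holds. Assumed holds are a 30% chance per round of 1–14 days.

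| Setting | All visit-dated | Half visit-dated |
|---|---|---|
| No offset | 15.3% | 15.3% |
| mSWAT visits | 27.0% | 18.0% |
| Adding a Cycle 2 mSWAT | 24.9% | 17.3% |
| Plain 12-week grid | 28.3% | 18.2% |
| mSWAT, no progression: censored at last assessment | 30.9% | 18.7% |
| mSWAT, 7-day windows | 22.7% | 17.1% |
| Scan windows | 21.0% | 16.6% |
| Half skin, half scan | 18.7% | 16.1% |
| mSWAT with holds | 20.0% | 16.6% |
| Skin/scan mix with holds | 17.3% | 15.8% |
| Heavier holds (50%, 1–28 days) | 17.0% | 15.6% |

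With a quarter visit-dated the rate is 15.8% (15.4% with holds); with none it is 15.1%. The average hazard ratio with no effect is 0.88–0.92 in the 25–31% settings, 0.93–0.98 with all visit-dated but wider windows, a mix or holds, and 0.97–1.00 when half or fewer are visit-dated. At a nominal 2.5% the rates for these three groups are 5.6–7.9%, 3.3–5.2% and 2.8–3.7%.

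**Step 4: cross-check.** Separate runs with 24 months of follow-up after accrual, 3-day windows and all progressions visit-dated give a mean Z towards the combination of 0.374 (calendar grid) and 0.488 (12-week grid). Then 1 − Φ(1.036 − 0.374) = 25.4% and 1 − Φ(1.036 − 0.488) = 29.2%, against simulated 25.6% and 28.9%. Without the offset both grids give 15.3%. Holds in 10–20% of cycles give 15–20%, and four-weekly detection gives 15–18%.

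**Step 5: candidate remedies.**
- *Timing from randomisation alone* (0–7 day lag to first dose): 25.8%/17.9% (all/half visit-dated), so it does not cure the problem.
- *Nonparametric interval-censored test on dates:* 27.7%, no cure.
- *Log-rank grouped by nominal round:* 13.0–13.3%. Power is 60.5% against 63.7% at hazard ratio 0.7, and 80.1% against 82.2% at 0.6.
- *Weibull interval-censored model:* 15.3–15.8%, power 65.6% and 83.1%, on simulated data that fit its shape.

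**The case against.** The best defence is that many progressions will not be visit-dated. Patients attend at least every two weeks and skin disease is visible. New tumours in patients without tumour-stage skin disease count as progression (Section 12.1.3). Patients without extracutaneous disease have no scheduled follow-up scans, and B0 patients have flow cytometry only at baseline, to confirm response, on suspicion of progression and at end of treatment. Clinical progression ends treatment (Section 6.4). Control patients can cross over on progression after two cycles (Section 6.6.1), which encourages unscheduled work-up. Permitted dose holds also blur the clusters. With holds and half or a quarter visit-dated, the rate is 15.4–16.6%. The null hazard ratio of 0.97–1.00 when half or fewer are visit-dated is small beside a standard error of the log hazard ratio of about 2/√82 = 0.22, even if all 82 patients progressed. In that range a round-grouped test at 13% is further from the 15.3% no-offset rate than the planned test is.

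All of this stands on size. A reader might take 25–31% as the expected error, but the documents do not support that: it needs 2–3 day windows for every progression, and the scan window in footnote g is far wider. A reader might also conclude that the log-rank should be replaced. The conservatism and power loss of the round-grouped test argue against that.

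The direction still stands, and the plan does not call for recording whether a progression was found on schedule, so the tilt could not be sized afterwards. The week origin is partly unclear, since the calendar heads the priming column as week 1. Counting Week 12 from priming would align the first round only; later rounds are set by cycle number, and the rates are then 24.5%/17.5% without holds and 18.4%/16.1% with holds.

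**Conclusion.** The offset is documented and its direction is certain; its size is not. At an assumed one-sided 15% level and a 7.7-month median, the false-positive rate for PFS is:
- about 25–31% only if every progression is visit-dated with 2–3 day windows and no holds;
- about 16–23% with 7-day or scan windows, a skin/scan mix, holds, or half visit-dated;
- about 15–16% if most progressions are found off schedule or holds are frequent.

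The visit-dated share, hold frequency, PFS level and censoring date are all assumptions. The median matters too. At 5 months, all/half visit-dated give 37%/20% without holds and 24%/17% with holds; at 11 months, 22%/17% and 18%/16%.

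A reader might infer that the primary result is also biased. It is not affected in this way: ORR6 depends on the time between two assessments in the same patient, so a constant 7-day shift cancels. The futility rule uses ORR6 and the safety rules use adverse events. This is a low-cost improvement to a secondary analysis, not a flaw in the trial's decision.

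**What to change.** In Section 9.4, keep the date-based log-rank and pre-specify beside it one PFS analysis that removes the offset:
- **Either** a log-rank grouped by nominal round: Week 12, Cycles 6, 9 and 12, then 12-week steps. Each round's mSWAT, flow cytometry and scan belong together, and the round closes at the end of the scan window. Progressions and deaths between rounds go to the next round. Patients censored at crossover, next therapy or last contact stay at risk through their last completed round. This rule must be written down, because dropping crossover patients from that round gives 26.5% error. A complementary log-log model can supply the hazard ratio.
- **Or** a parametric interval-censored model.

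State that a PFS advantage seen only in the date-based log-rank will not be read as a drug effect. Give the PFS level, sidedness and censoring date. Record for each progression whether it was found at a scheduled or an unscheduled assessment.

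The cost is one extra analysis, some wording and one data field, with no change to visits or treatment. The round-grouped test is slightly conservative (about 13%, because the combination's first round is a week longer) and costs about 2–4 points of power, so it should not simply replace the log-rank. The Weibull model holds its level but assumes a baseline shape.

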13. STUDY OVERSIGHT AND DATA REPORTING / REGULATORY REQUIREMENTS

Adverse event lists, guidelines, and instructions for AE reporting can be found in Section 10 (Adverse Events: List and Reporting Requirements).

13.1 Study Oversight

This protocol is monitored at several levels, as described in this section. The Protocol Principal Investigator is responsible for monitoring the conduct and progress of the clinical trial, including the ongoing review of accrual, patient-specific clinical and laboratory data, and routine and serious adverse events; reporting of expedited adverse events; and accumulation of reported adverse events from other trials testing the same drug(s). The Protocol Principal Investigator and statistician have access to the data at all times through the CTMS web-based reporting portal.

For the Phase 1 portion of this study, all decisions regarding dose escalation/expansion/de-escalation require sign-off by the Protocol Principal Investigator through the CTMS/IWRS. In addition, for the Phase 1 portion, the Protocol Principal Investigator will have at least monthly, or more frequently, conference calls with the Study Investigators and the CTEP Medical Officer(s) to review accrual, progress, and adverse events and unanticipated problems.

For a Phase 1/2 trial, enrollment to the Phase 2 portion of the trial will not begin until a protocol amendment has been submitted which summarizes the Phase 1 results, the recommended Phase 2 dose, and the rationale for selecting it. The amendment must be reviewed and approved by CTEP before enrollment to the Phase 2 portion can begin.

All Study Investigators at participating sites who register/enroll patients on a given protocol are responsible for timely submission of data via Medidata Rave and timely reporting of adverse events for that particular study. This includes timely review of data collected on the electronic CRFs submitted via Medidata Rave.

All studies are also reviewed in accordance with the enrolling institution's data safety monitoring plan.

13.2 Data Reporting

Medidata Rave is the clinical data management system being used for data collection for this trial/study. Access to the trial in Rave is controlled through the CTEP-IAM system and role assignments.

Requirements to access Rave via iMedidata:

NCI Protocol #: 10384

Version Date: September 5, 2023

- Active CTEP registration with credentials necessary to access secure NCI/CTSU IT systems, and
- Assigned a Rave role on the LPO or PO roster at the enrolling site of: Rave CRA, Rave Read Only, Rave CRA (LabAdmin), Rave SLA, or Rave Investigator.

Rave role requirements:

- Rave CRA or Rave CRA (Lab Admin) role, must have a minimum of an Associate Plus (AP) registration type,
- Rave Investigator role, must be registered as a Non-Physician Investigator (NPIVR) or Investigator (IVR), and
- Rave Read Only or Rave SLA role must have at a minimum an Associates (A) registration type.

- Refer to <https://ctep.cancer.gov/investigatorResources/default.htm> for registration types and documentation required.

If the study has a Delegation of Tasks Log (DTL), individuals requiring write access to Rave must also be assigned the appropriate Rave tasks on the DTL.

Upon initial site registration approval for the study in the Regulatory application, all persons with Rave roles assigned on the appropriate roster will be sent a study invitation email from iMedidata. To accept the invitation, site staff must either click on the link in the email or log in to iMedidata via the CTSU members' website under *Data Management > Rave Home* and click to accept the invitation in the Tasks pane located in the upper right-corner of the iMedidata screen. Site staff will not be able to access the study in Rave until all required Medidata and study specific trainings are completed. Trainings will be in the form of electronic learnings (eLearnings) and can be accessed by clicking on the eLearning link in the *Tasks* pane located in the upper right corner of the iMedidata screen. If an eLearning is required for a study and has not yet been taken, the link to the eLearning will appear under the study name in the *Studies* pane located in the center of the iMedidata screen; once the successful completion of the eLearning has been recorded, access to the study in Rave will be granted, and a *Rave EDC* link will replace the eLearning link under the study name.

Site staff who have not previously activated their iMedidata/Rave account at the time of initial site registration approval for the study in the Regulatory application will receive a separate invitation from iMedidata to activate their account. Account activation instructions are located on the CTSU website in the Data Management section under the Rave resource materials (Medidata Account Activation and Study Invitation Acceptance). Additional information on iMedidata/Rave is available on the CTSU members' website in the Data Management > Rave section or by contacting the CTSU Help Desk at [name] or by e-mail at [contact].

